5.3.1 Hepatotoxicity Assessment

Hepatotoxicity will be monitored using weekly liver function tests (LFTs) including AST, ALT, alkaline phosphatase, total bilirubin, and GGT during the 6 cycles where subjects are receiving combined treatment with urelumab and nivolumab (Table 5.1-2), and also weekly for the first 8 weeks following the last dose with urelumab. Following this period of weekly assessments, LFTs will also be monitored at all 3 clinical/safety follow-up visits (Table 5.1-3). A management algorithm for the monitoring and management of hepatotoxicity is included in Appendix 3.

5.3.2 Imaging Assessment for the Study

Any incidental findings of potential clinical relevance that are not directly associated with the objectives of the protocol should be evaluated and handled by the Study Investigator as per standard medical/clinical judgment.

5.3.3 Laboratory Test Assessments

A local laboratory will perform the analyses and will provide reference ranges for these tests. Results of clinical laboratory tests performed on Day -1 or Day -2 must be available prior to dosing.

The following clinical laboratory tests will be performed:

Hematology

CBC with differential and platelets

Serum Chemistry

Aspartate aminotransferase (AST)

Total Protein

Alanine aminotransferase (ALT)

Albumin

Total bilirubin

Sodium

Alkaline phosphatase

Potassium

Lactate dehydrogenase (LDH)

Chloride

Gamma-glutamyl transferase (GGT)

Carbon dioxide

Creatinine

Calcium

Blood Urea Nitrogen (BUN)

Phosphorus

Glucose (Fasting at screen visit)

C-reactive protein (CRP)

Ferritin

Magnesium

Amylase

Uric Acid

Lipase

Urinalysis

Protein

Glucose

Blood

Leukocyte esterase

Specific gravity

pH

Microscopic examination of the sediment if blood, protein or leukocytes esterase are positive on the dipstick

Serology

Serum for hepatitis C antibody, hepatitis C viral load, hepatitis B surface antigen, Hepatitis A IgM, HIV-1, -2 antibody, HPV status (screening only); HIV-1, -2 antibody at sites where mandated at screening only

Other Analyses

Protime(PT)/Prothrombin Time (PTT)

Thyroid Function Tests: Free T4, Free T3 and TSH

Pregnancy test (WOCBP only: screening, during dosing at predose and at a minimum of every 4 weeks, as well as Day 30, 60 and 100 follow-up visits).

Clinical laboratories will be assessed (see [Table 5.1-1](#), [Table 5.1-2](#), [Table 5.1-3](#), [Table 5.1-4](#), [Table 5.1-5](#), and [Table 5.1-6](#)).

Sites should collect these samples between -28 to -1 days from registration to ensure that results required for eligibility purposes are verified prior to registration. Pregnancy testing must be performed at screening, within 24 hours prior to each administration of study drug and at a minimum of every 4 weeks in the event of dosing delays. In addition pregnancy testing should be performed at Day 30, 60 and 100 follow-up visits. CBC plus differential and serum chemistry panel should be drawn within 72 hours prior to each subsequent scheduled cycle. On-study laboratory tests will be performed on site/locally. Laboratory tests may be obtained more frequently if indicated. Additional laboratory tests should be performed as per standard of care.

Laboratory toxicities (eg, suspected drug induced liver enzyme elevations) will be monitored during the Clinical/Safety Follow-up period via on site/local labs until all study drug related toxicities resolve, return to baseline, or are deemed irreversible.

C3D29	0 h (pre-dose)	00:00	X	X	X	X
C3D36	168 h	168:00	X		X	
C3D43	0 h (pre-dose)	00:00	X		X	
C4D1	0 h (pre-dose)	00:00	X	X	X	X
C5D1	0 h (pre-dose)	00:00	X	X	X	X
C6D1	0 h (pre-dose)	00:00	X	X	X	X
30 Day Follow-Up			X	X	X	X
60 Day Follow-Up ^c			X	X	X	X

Table 5.5.1-1: Pharmacokinetic Sampling Schedule (Dose Escalation)

Study Day	Event	Time (relative to Nivolumab dosing)	Urelumab		Nivolumab	
			PK Sample	ADA Sample	PK Sample	ADA Sample
100 Day Follow-Up ^c			X	X	X	X

^a All subsequent urelumab predose samples can be collected at same time as the nivolumab predose sample

^b EOI: End of infusion. This sample should be taken immediately prior to stopping the infusion (preferably within 2 minutes prior to the end of infusion). If the end of infusion is delayed to beyond the normal infusion duration of 1 hour, the collection of this sample should be delayed accordingly. Urelumab predose samples can be collected at same time as the nivolumab predose sample.

^c If a subject permanently discontinues study drug treatment during the sampling period, they will move to sampling at the follow-up visits.

Table 5.5.1-2: Pharmacokinetic Sampling Schedule (First 6 Subjects in Stage 1 Expansion)

Study Day	Event	Time (relative to Nivolumab dosing)	Urelumab		Nivolumab	
			PK Sample	ADA Sample	PK Sample	ADA Sample
C1D1	0 h (pre-dose) ^a	00:00	X	X	X	X
	1 h (EOI nivolumab) ^b	01:00			X	
	2 h (EOI urelumab) ^b	02:00	X			
	4 h	04:00	X		X	
	6 h	06:00	X		X	
C1D8	168 h	168:00	X		X	
C1D15	0 h (pre-dose)	00:00	X		X	
C1D29	0 h (pre-dose)	00:00	X	X	X	X
C2D1	0 h (pre-dose)	00:00	X	X	X	X
C3D1	0 h (pre-dose)	00:00	X		X	
	1 h (EOI nivolumab) ^b	01:00			X	
	2 h (EOI urelumab) ^b	02:00	X			
C3D8	168 h	168:00	X			
C3D15	0 h (pre-dose)	00:00	X			
C3D29	0 h (pre-dose)	00:00	X			
C4D1	0 h (pre-dose)	00:00	X	X	X	X
C6D1	0 h (pre-dose)	00:00	X	X	X	X
60 Day Follow-Up ^c			X	X	X	X
100 Day Follow-Up ^c			X	X	X	X

^a All subsequent urelumab predose samples can be collected at same time as the nivolumab predose sample

^b EOI: End of infusion. This sample should be taken immediately prior to stopping the infusion (preferably within 2 minutes prior to the end of infusion). If the end of infusion is delayed to beyond the normal infusion duration of 1 hour, the collection of this sample should be delayed accordingly. Urelumab predose samples can be collected at same time as the nivolumab predose sample.

^c If a subject permanently discontinues study drug treatment during the sampling period, they will move to sampling at the follow-up visits.

Table 5.5.1-3: Pharmacokinetic Sampling Schedule (After 6 subject in Stage 1 Expansion, all subjects in Stage 2 Expansion and Retreatment)

Study Day	Event	Time (relative to Nivolumab dosing)	Urelumab		Nivolumab	
			PK Sample	ADA Sample	PK Sample	ADA Sample
C1D1	0 h (pre-dose) ^a	00:00	X	X	X	X
	1 h (EOI nivolumab) ^b	01:00			X	
	2 h (EOI urelumab) ^b	02:00	X			
C1D29	0 h (pre-dose)	00:00	X	X	X	X
C2D1	0 h (pre-dose)	00:00	X	X	X	X
C3D1	0 h (pre-dose)	00:00	X		X	
	1 h (EOI nivolumab) ^b	01:00			X	
	2 h (EOI urelumab) ^b	02:00	X			
C4D1	0 h (pre-dose)	00:00	X	X	X	X
C6D1	0 h (pre-dose)	00:00	X	X	X	X
60 Day Follow-Up ^c			X	X	X	X
100 Day Follow-Up ^c			X	X	X	X

^a All subsequent urelumab predose samples can be collected at same time as the nivolumab predose sample.

^b EOI: End of infusion. This sample should be taken immediately prior to stopping the infusion (preferably within 2 minutes prior to the end of infusion). If the end of infusion is delayed to beyond the normal infusion duration of 1 hour, the collection of this sample should be delayed accordingly. Urelumab predose samples can be collected at same time as the nivolumab predose sample.

^c If a subject permanently discontinues study drug treatment during the sampling period, they will move to sampling at the follow-up visits.

Table 5.5.1-4: Pharmacokinetic Sampling Schedule (Subjects with Melanoma PD-L1 negative)

[figure not shown]
Study Day	Event	Time (relative to Nivolumab dosing)	Urelumab		Nivolumab	
			PK Sample	ADA Sample	PK Sample	ADA Sample
C1D1	0 h (pre-dose) ^a	00:00	X	X	X	X
	1 h (EOI nivolumab) ^b	01:00			X	
	2 h (EOI urelumab) ^b	02:00	X			
C1D29	0 h (pre-dose)	00:00	X	X	X	X
C2D1	0 h (pre-dose)	00:00	X	X	X	X
C3D1	0 h (pre-dose)	00:00	X		X	
	1 h (EOI nivolumab) ^b	01:00			X	
	2 h (EOI urelumab) ^b	02:00	X			
C4D1	0 h (pre-dose)	00:00	X	X	X	X
C6D1	0 h (pre-dose)	00:00	X	X	X	X
60 Day Follow-Up ^c			X	X	X	X
100 Day Follow-Up ^c			X	X	X	X

^a All subsequent urelumab predose samples can be collected at same time as the nivolumab predose sample.

^b EOI: End of infusion. This sample should be taken immediately prior to stopping the infusion (preferably within 2 minutes prior to the end of infusion). If the end of infusion is delayed to beyond the normal infusion duration of 1 hour, the collection of this sample should be delayed accordingly. Urelumab predose samples can be collected at same time as the nivolumab predose sample.

^c If a subject permanently discontinues study drug treatment during the sampling period, they will move to sampling at the follow-up visits.

[REDACTED]

[REDACTED]

[REDACTED]

[REDACTED]

[REDACTED]

6 ADVERSE EVENTS

An *Adverse Event(AE)* is defined as any new untoward medical occurrence or worsening of a preexisting medical condition in a clinical investigation subject administered study drug and that does not necessarily have a causal relationship with this treatment. An AE can therefore be any unfavorable and unintended sign (such as an abnormal laboratory finding), symptom, or disease temporally associated with the use of study drug, whether or not considered related to the study drug.

The causal relationship to study drug is determined by a physician and should be used to assess all adverse events (AE). The causal relationship can be one of the following:

Related: There is a reasonable causal relationship between study drug administration and the AE.

Not related: There is not a reasonable causal relationship between study drug administration and the AE.

The term “reasonable causal relationship” means there is evidence to suggest a causal relationship.

Adverse events can be spontaneously reported or elicited during open-ended questioning, examination, or evaluation of a subject. (In order to prevent reporting bias, subjects should not be questioned regarding the specific occurrence of one or more AEs.)

6.1 Serious Adverse Events

A *Serious Adverse Event (SAE)* is any untoward medical occurrence that at any dose:

- results in death
- is life-threatening (defined as an event in which the subject was at risk of death at the time of the event; it does not refer to an event which hypothetically might have caused death if it were more severe)
- requires inpatient hospitalization or causes prolongation of existing hospitalization (see **NOTE** below)

- results in persistent or significant disability/incapacity
- is a congenital anomaly/birth defect
- is an important medical event (defined as a medical event(s) that may not be immediately life-threatening or result in death or hospitalization but, based upon appropriate medical and scientific judgment, may jeopardize the subject or may require intervention [eg, medical, surgical] to prevent one of the other serious outcomes listed in the definition above). Examples of such events include, but are not limited to, intensive treatment in an emergency room or at home for allergic bronchospasm; blood dyscrasias or convulsions that do not result in hospitalization). Potential drug induced liver injury (DILI) is also considered an important medical event. (See [Section 6.6](#) for the definition of potential DILI).

Suspected transmission of an infectious agent (eg, pathogenic or nonpathogenic) via the study drug is an SAE.

Although pregnancy, overdose, cancer, and potential drug induced liver injury (DILI) are not always serious by regulatory definition, these events must be handled as SAEs. (See [Section 6.1.1](#) for reporting pregnancies).

Any component of a study endpoint that is considered related to study therapy (eg, death is an endpoint, if death occurred due to anaphylaxis, anaphylaxis must be report) should be reported as SAE (see [Section 6.1.1](#) for reporting details).

NOTE:

The following hospitalizations are not considered SAEs in BMS clinical studies:

- a visit to the emergency room or other hospital department < 24 hours, that does not result in admission (unless considered an important medical or life-threatening event)
- elective surgery, planned prior to signing consent
- admissions as per protocol for a planned medical/surgical procedure
- routine health assessment requiring admission for baseline/trending of health status (eg, routine colonoscopy)
- medical/surgical admission other than remedying ill health state and planned prior to entry into the study. Appropriate documentation is required in these cases
- admission encountered for another life circumstance that carries no bearing on health status and requires no medical/surgical intervention (eg, lack of housing, economic inadequacy, care-giver respite, family circumstances, administrative)
- admission for administration of anticancer therapy in the absence of any other SAEs.

6.1.1 *Serious Adverse Event Collection and Reporting*

The Investigator Brochures (IB) represent the Reference Safety Information to determine expectedness of serious adverse events for expedited reporting. Following the subject's written consent to participate in the study, all SAEs, whether related or not related to study drug, must be collected, including those thought to be associated with protocol-specified procedures. All SAEs

must be collected that occur during the screening period and within 100 days of discontinuation of dosing. If applicable, SAEs must be collected that relate to any later protocol-specified procedure (eg, a follow-up skin biopsy).

The investigator should report any SAE occurring after these time periods that is believed to be related to study drug or protocol-specified procedure.

An SAE report should be completed for any event where doubt exists regarding its seriousness.

If the investigator believes that an SAE is not related to study drug, but is potentially related to the conditions of the study (such as withdrawal of previous therapy, or a complication of a study procedure), the relationship should be specified in the narrative section of the SAE Report Form.

SAEs, whether related or not related to study drug, and pregnancies must be reported to BMS (or designee) within 24 hours. SAEs must be recorded on the SAE Report Form; pregnancies on a Pregnancy Surveillance Form (electronic or paper forms). The preferred method for SAE data reporting collection is through the eCRF. The paper SAE/pregnancy surveillance forms are only intended as a back-up option when the eCRF system is not functioning. In this case, the paper forms are to be transmitted via email or confirmed facsimile (fax) transmission to:

SAE Email Address: Refer to Contact Information list.

SAE Facsimile Number: Refer to Contact Information list.

For studies capturing SAEs through electronic data capture (EDC), electronic submission is the required method for reporting. The paper forms should be used and submitted immediately, only in the event the electronic system is unavailable for transmission. When paper forms are used, the original paper forms are to remain on site.

SAE Telephone Contact (required for SAE and pregnancy reporting): See Contact Information list.

If only limited information is initially available, follow-up reports are required. (Note: Follow-up SAE reports should include the same investigator term(s) initially reported.)

If an ongoing SAE changes in its intensity or relationship to study drug or if new information becomes available, a follow-up SAE report should be sent within 24 hours to BMS (or designee) using the same procedure used for transmitting the initial SAE report.

All SAEs should be followed to resolution or stabilization.

6.2 Nonserious Adverse Events

A *nonserious adverse event* is an AE not classified as serious.

6.2.1 Nonserious Adverse Event Collection and Reporting

The collection of nonserious AE information should begin at initiation of study drug. Nonserious AE information should also be collected from the start of a placebo lead-in period or other observational period intended to establish a baseline status for the subjects.

Nonserious AEs should be followed to resolution or stabilization, or reported as SAEs if they become serious (see [Section 6.1.1](#)). Follow-up is also required for nonserious AEs that cause interruption or discontinuation of study drug and for those that are present at the end of study treatment as appropriate. All identified nonserious AEs must be recorded and described on the nonserious AE page of the CRF (paper or electronic).

All nonserious adverse events (not only those deemed to be treatment-related) should be collected continuously during the treatment period and for a minimum of 100 days following the last dose of study treatment.

Completion of supplemental CRFs may be requested for AEs and/or laboratory abnormalities that are reported/identified during the course of the study.

6.3 Laboratory Test Result Abnormalities

The following laboratory test result abnormalities should be captured on the nonserious AE CRF page or SAE Report Form (paper or electronic) as appropriate:

- Any laboratory test result that is clinically significant or meets the definition of an SAE
- Any laboratory test result abnormality that required the subject to have study drug discontinued or interrupted
- Any laboratory test result abnormality that required the subject to receive specific corrective therapy.

It is expected that wherever possible, the clinical, rather than laboratory term would be used by the reporting investigator (eg, anemia versus low hemoglobin value).

6.4 Pregnancy

If, following initiation of the investigational product, it is subsequently discovered that a study subject is pregnant or may have been pregnant at the time of study exposure, including during at least 5 half lives after product administration, the investigator must immediately notify the BMS Medical Monitor/designee of this event and complete and forward a Pregnancy Surveillance Form to BMS Designee within 24 hours and in accordance with SAE reporting procedures described in [Section 6.1.1](#).

In most cases, the study drug will be permanently discontinued in an appropriate manner (eg, dose tapering if necessary for subject safety).

In the rare event that the benefit of continuing study drug is thought to outweigh the risk, after consultation with BMS, the pregnant subject may continue study drug after a thorough discussion of benefits and risk with the subject.

Protocol-required procedures for study discontinuation and follow-up must be performed on the subject unless contraindicated by pregnancy (eg, x-ray studies). Other appropriate pregnancy follow-up procedures should be considered if indicated.

The investigator must immediately notify the BMS Medical Monitor (or designee) of this event and complete and forward a Pregnancy Surveillance Form to BMS (or designee) within 24 hours and in accordance with SAE reporting procedures described in [Section 6.1.1](#).

Follow-up information regarding the course of the pregnancy, including perinatal and neonatal outcome and, where applicable, offspring information must be reported on the Pregnancy Surveillance Form.

Any pregnancy that occurs in a female partner of a male study participant should be reported to BMS. Information on this pregnancy will be collected on the Pregnancy Surveillance Form.

6.5 Overdose

An overdose is defined as the accidental or intentional administration of any dose of a product that is considered both excessive and medically important. All occurrences of overdose must be reported as an SAE (see [Section 6.1.1](#) for reporting details).

6.6 Potential Drug Induced Liver Injury (DILI)

Wherever possible, timely confirmation of initial liver-related laboratory abnormalities should occur prior to the reporting of a potential DILI event. All occurrences of potential DILIs, meeting the defined criteria, must be reported as SAEs (see [Section 6.1.1](#) for reporting details).

Potential drug induced liver injury is defined as:

- 1) Aminotransferase (ALT or AST) elevation > 3 times upper limit of normal (ULN)
AND
- 2) Total bilirubin > 2 times ULN, without initial findings of cholestasis (elevated serum alkaline phosphatase),
AND
- 3) No other immediately apparent possible causes of AT elevation and hyperbilirubinemia, including, but not limited to, viral hepatitis, pre-existing chronic or acute liver disease, or the administration of other drug(s) known to be hepatotoxic.

6.7 Other Safety Considerations

Any significant worsening noted during interim or final physical examinations, electrocardiograms, x-ray filming, any other potential safety assessments required or not required by the protocol should also be recorded as a nonserious or serious AE, as appropriate, and reported accordingly.

6.7.1 Treatment Algorithms for Drug-related Adverse Events

Treatment algorithms for the management of potential drug-related adverse events are located in [Appendix 3](#).

6.7.2 *Rapid Notification of Other Adverse Events of Interest*

In addition to serious adverse events, overdose, and pregnancy, the following adverse events will also be reported on an expedited basis to the BMS Medical Monitor or Study Director by phone or e-mail:

- Adverse events that potentially meet DLT criteria; see [section 4.5.2](#)
- Any potential Hy's Law case ($> 3 \times$ ULN of either ALT/AST with concurrent $> 2 \times$ ULN of Total Bilirubin and no alternate etiology)
- \geq Grade 2 study-drug related adverse events (including neurologic toxicity)
- \geq Grade 2 diarrhea/colitis
- \geq Grade 3 motor neurologic toxicity regardless of causality

7 *DATA MONITORING COMMITTEE AND OTHER EXTERNAL COMMITTEES*

Not applicable

8 *STATISTICAL CONSIDERATIONS*

8.1 *Sample Size Determination*

8.1.1 *Dose Escalation*

In dose escalation, the sample size at each dose cannot be determined exactly, as it depends on the number of observed toxicities. Between 3 and 12 subjects approximately are expected to be treated during dose escalation in each dose level.

8.1.2 *Cohort Expansion*

8.1.2.1 *Stage 1*

During Stage 1 of cohort expansion, approximately 20 subjects in each tumor type will be treated at the MTD/HAD dose level and schedule. A sample size of approximately 20 subjects in each tumor type in Stage 1 is intended to provide a better picture of the safety of each regimen. For example, if a low grade adverse event were observed in 3 or fewer patients, the 90% 1-sided upper confidence interval would be 30%. In addition, it allows for a futility assessment. In general, if the true response rate is 20%, 30%, 40%, or 50%, the probability of seeing 4 or more responses in the 20 patients is 58.9%, 89.3%, 98.4%, and 99.9%, respectively. If the true response rate is 30%, the likelihood of seeing less than 4/20 responses is 10.7% (false negative rate). Conversely, if the true response rate is 10%, the likelihood of seeing 4 or more responses is 13.3% (false positive rate).

8.1.2.2 *Stage 2:*

During Stage 2 of cohort expansion, up to approximately 20 additional subjects will be treated in each tumor type. This will allow for further establishment of the safety profile of the combination and a preliminary assessment of efficacy. The total of approximately 40 subjects (20 from Stage 1 Expansion and 20 from Stage 2) is designed to provide higher precision around estimates of safety and preliminary efficacy. If in a cohort of 40 subjects 7, 10, or 15 responses are observed, then the

lower limit of the one-sided 90% exact binomial CI for the ORR is 10%, 16%, and 27% respectively. These calculations are made using the Clopper-Pearson method for exact confidence intervals. If the true ORR in a tumor type is 50%, then with 40 subjects in a tumor type, there is 96% chance of observing at least 15 responses, and 87% chance of observing at least 17 responses, and there is 8% chance of observing 15 or fewer responses (false negative rate).

An additional 50 treatment naïve PD-L1 negative melanoma subjects will be treated at MTD/HAD to further evaluate if there is an efficacy signal in this population. Additional subjects may be enrolled and treated so as to accrue a minimum of 50 evaluable subjects with at least 2 on treatment scans. These 50 PD-L1 negative melanoma patients will be combined for analysis with approximately 18 PD-L1 negative melanoma patients from Cohort 2 for a total of 68 PD-L1 negative melanoma patients. Assuming an ORR of approximately 56%, a minimum of 38/68 responders would provide a 95% Clopper-Pearson confidence interval with a lower limit above 42%.

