Amendment 08	22-Mar-2017	In order to further explore an emerging efficacy signal, additional patients with previously untreated metastatic melanoma (ie, no prior systemic anticancer therapy for unresectable or metastatic melanoma) subjects with PD-L1 negative tumors (<1%) will be enrolled under this amendment.
Revised Protocol 05	09-May-2016	Incorporates Amendment 06 and Administrative Letters 04 and 05
Amendment 06	09-May-2016	To include a cohort of NSCLC and melanoma subjects who have relapsed or are refractory to prior anti-PD-1/anti-PD-L1 therapy.
Administrative Letter 05	01-Jun-2016	To clarify application to new cohort of subjects with NSCLC and melanoma who have relapsed or are refractory to prior anti-PD-1/anti-PD-L1) therapy and exception for NSCLC and MEL subjects enrolling in the expansion cohorts where prior anti-PD-1 or anti-PD-L1 therapies are specifically required.
Administrative Letter 04	19-Jan-2016	Change in MM
Revised Protocol 04	22-Dec-2015	Incorporates Amendment 05
Amendment 05	22-Dec-2015	To expand the study population for cohort expansion to include subjects with follicular lymphoma and to further differentiate subjects with non-small-cell lung cancer into two separate groups (those with no prior anti PD-1/anti-PD-L1 therapy and those who have relapsed or are refractory to prior anti-PD-1/anti-PD-L1).
Revised Protocol 03	30-Aug-2015	Incorporates Amendment 04 and Administrative Letter 03
Amendment 04	30-Aug-2015	Discontinue enrollment into Cohorts A, B, C, D. Implement an update to exclusion Criteria
Admin Letter 03	26-Aug-2015	Discontinue enrollment into Cohorts A, B, C, D during cohort expansion
Revised Protocol 02	29-Jun-2015	Incorporates Amendment 03
Amendment 03	29-Jun-2015	To implement a change in duration to combination therapy and use of flat dosing for subjects enrolled following approval of Revised Protocol 02
Revised Protocol 01	06-Mar-2015	Incorporate Amendment 02
Amendment 02	06-Mar-2015	To implement changes to inclusion/exclusion criteria, clarify requirements and assessments for treatment beyond disease progression and criteria for allowing treatment to resume after a dose delay due to toxicity, add time and events schedules for subjects eligible for retreatment, and clarify PK sampling and biomarker assessments.

Document	Date of Issue	Summary of Change

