Stage 2: During Stage 2 of cohort expansion, up to approximately 20 additional subjects will be treated in each tumor type. This will allow for further establishment of the safety profile of the combination and a preliminary assessment of efficacy. A total of 40 subjects (20 from Stage 1 and 20 from Stage 2) is based on achieving a higher precision. If in a cohort of 40 subjects 12, 15, or 18 responses are observed, then the lower limit of the one-sided 90% exact binomial CI for the ORR is 20%, 27%, and 34% respectively. These calculations are based on the Clopper-Pearson method for exact confidence intervals. If the true ORR in a tumor type is 50%, then with 40 subjects in a tumor type there is 96% chance of observing at least 15 responses, and 87% chance of observing at least 17 responses, and there is 8% chance of observing 15 or fewer responses (false negative rate).

[figure not shown]
An additional 50 treatment naïve PD-L1 negative melanoma subjects will be treated at MTD/HAD to further evaluate if there is an efficacy signal in this population. Additional subjects may be enrolled and treated so as to accrue a minimum of 50 evaluable subjects with at least 2 on treatment scans. These 50 PD-L1 negative melanoma patients will be combined for analysis with approximately 18 PD-L1 negative melanoma patients from Cohort 2 for a total of 68 PD-L1 negative melanoma patients. Assuming an ORR of approximately 56%, a minimum of 38/68 responders would provide a 95% Clopper-Pearson confidence interval with a lower limit above 42%.

Endpoints:

Primary Endpoint: Safety as measured by the rate of adverse events (AEs) and serious adverse events (SAEs), is the primary endpoint of this Phase 1/2 study. All subjects who receive at least one (full or partial) dose of urelumab or nivolumab will be evaluated for safety during treatment and for up to 100 days in follow-up.

Secondary Endpoints:

- **Efficacy:** Best overall response (BOR), objective response rate (ORR), duration of response, and progression free survival rate (PFSR) will be assessed based on RECIST v1.1 in subjects with solid tumors, and based on investigator assessment per revised IWG criteria in subjects with lymphomas.

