Preliminary data in 138 patients treated with urelumab and nivolumab as of the clinical cutoff date of 30-Sep-2016, revealed that the most frequent TRAE was fatigue (31%); grade 3/4 ALT/AST elevations (2%/2%) and TRAEs leading to discontinuation (6%) were infrequent. No treatment-related deaths were reported. Twenty-five of 124 evaluable patients treated with the combination had objective responses (melanoma, n=23; SCCHN, n=1, NSCLC, n=1). The ORR in melanoma was 50% (23/46) including 9/18 of subjects with PD-L1 negative tumors by IHC.

There remains a significant unmet need for curative options in the tumor types being evaluated in this study including PD-L1 negative melanoma where the objective response rate to anti-PD-1 monotherapy is ~30-35%. Overall, the data indicate a favorable benefit/risk profile for the evaluation of a combination of urelumab with nivolumab in this study since the availability of more effective therapies or combination of agents would be of great benefit to these patients with advanced cancer.

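### Report the new PD-L1-negative melanoma cohort on its own beside the pooled 68: if the 18 added subjects are the 9/18 already seen, the pooled ORR reads 4 to 5 points high at a true 30-35%

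*Protocol*

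**What the plan says.** Document History, Amendment 08 (22-Mar-2017), gives the reason for adding previously untreated PD-L1-negative melanoma: "In order to further explore an emerging efficacy signal".

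Protocol 8.1.2.2 (Stage 2) and the Synopsis plan 50 new subjects and a combined analysis: "These 50 PD-L1 negative melanoma patients will be combined for analysis with approximately 18 PD-L1 negative melanoma patients from Cohort 2". The total is 68. Assuming an ORR of about 56%, the stated precision is that "a minimum of 38/68 responders would provide a 95% Clopper-Pearson confidence interval with a lower limit above 42" per cent. No precision is stated for the new 50 alone.

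Protocol 1.5 reports "Preliminary data in 138 patients treated with urelumab and nivolumab as of the clinical cutoff date of 30-Sep-2016", and within them: "The ORR in melanoma was 50% (23/46) including 9/18 of subjects with PD-L1 negative tumors by IHC". The same section gives the background: "PD-L1 negative melanoma where the objective response rate to anti-PD-1 monotherapy is ~30-35" per cent.

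The Synopsis says that there is no formal primary hypothesis to test. SAP 2.4 incorporates amendments only up to 05, and the tumour categories in SAP 7.1 have no PD-L1-negative melanoma group.

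**The concern.** A cohort opened because of a result already in hand should be judged mainly on subjects who did not produce that result. The 18 match the 9/18 of section 1.5 in number, tumour and PD-L1 status, and the 30-Sep-2016 cutoff falls about six months before Amendment 08. If they are the same subjects, 18 of the 68 in the estimate have a known outcome of 50%, and only 50 can still inform the question.

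With no formal test, the point estimate and interval are the result. A reader will set them against the protocol's own 30-35% for monotherapy. If the combination adds nothing, the earlier 18 pull the pooled figure up and can lift its lower limit above the background rate when the new data alone would not.

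**Working it through.** **Inputs.** 50 new plus about 18 earlier subjects; 38/68; 95% Clopper-Pearson; planning ORR 56% (Protocol 8.1.2.2). Earlier result 9/18 and background 30-35% (Protocol 1.5). Two-sided interval (SAP 7.5). Assumption: the 18 are the 9/18.

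**The plan's own figure.** 38/68 = 55.9%, with 95% limits of 43.3% to 67.9% (width 24.6 points). 37/68 has a lower limit of 41.9%. So 38 is the minimum for a lower limit above 42%, and the protocol is right.

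**Bias with 9/18 fixed.** The expected pooled ORR at a true rate p is (9 + 50p)/68. The bias is that minus p, which equals (18/68)(0.50 - p).
- p = 30%: (9 + 15)/68 = 35.3%, bias +5.3 points
- p = 35%: (9 + 17.5)/68 = 39.0%, bias +4.0
- p = 50%: bias 0
- p = 56%: (9 + 28)/68 = 54.4%, bias -1.6

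**How often the lower limit exceeds the truth (nominal at most 2.5%).**
- Truth 30%: the pool needs 29/68, so 20 new responders. P(Y ≥ 20 | 50, 0.30) = 8.5%. The new 50 alone need 23, probability 1.2%. For 68 entirely fresh subjects it would be 1.8%.
- Truth 35%: the pool needs 33/68, so 24 new responders, probability 4.0%. The new 50 alone need 25, probability 2.1%. For 68 fresh subjects, 1.5%.

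**Sensitivity to the earlier count.** The text says about 18, and counts may change after a cutoff. With 8/18 or 10/18 the lower-limit miss is 4.8% or 14.1% at a true 30%, and 2.1% or 7.1% at 35%. This range does not cover a different set of subjects.

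**An example.** Suppose that 20 of the new 50 respond. Alone this is 40.0% (26.4% to 54.8%), which includes 30%. Pooled it is 29/68 = 42.6% (30.7% to 55.2%), which excludes 30%.

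**The 42% benchmark.** With 9/18 fixed, 38/68 needs 38 - 9 = 29 new responders. For the new cohort alone, 28/50 has a lower limit of 41.3% and 29/50 gives 43.2% to 71.8% (width 28.6), so 29 are needed there too. The chance of 29 or more is 0.004% at a true 30% and 0.075% at 35%.

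**Accuracy of the point estimate.** Root-mean-square error in points with 9/18 fixed, pooled against new 50 alone: 7.1 against 6.5 at 30%; 6.4 against 6.7 at 35%; 5.7 against 6.9 at 40%; 5.2 against 7.1 at 50%; 5.4 against 7.0 at 56%. Pooling is better when 324(0.5 - p)² < 42.48p(1 - p), that is, for p from about 33% to 67%.

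**The case against.** Several points on the other side have force.

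- **The link is inferred.** No text says that the 18 from Cohort 2 are the 9/18. Section 1.5 covers all 138 combination-treated patients and names neither Cohort 2 nor untreated disease. The cohort of melanoma after anti-PD-1 therapy (Amendment 06, 09-May-2016) also pre-dates the cutoff. This stands, and without the link the bias figures do not apply.
- **30-35% is the adverse case.** It means that the combination adds nothing. Nine or more of 18 would then occur with probability 6.0% (true 30%) or 13.9% (true 35%). At the planned 56% the pool reads slightly low. This stands.
- **Pooling is a legitimate trade-off.** It is declared in advance, and it gives the smaller root-mean-square error over the middle of the range. This stands as a reason to keep the pooled figure. It does not restore coverage near 30%, and declaring the pooling does not make data already seen new.
- **A separate estimate may already be implied.** The cohort has its own row in the expansion table (Protocol 3.1.6), and Protocol 8.4.2 gives ORR by tumour type. That is a fair reading, but the only ORR analysis spelled out for this cohort is the pooled one. The SAP's silence reflects its date, and its PD-L1 section (7.8.1) is not visible.

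Two stronger readings are tempting. A reader might infer that pooling makes the target easier to hit. It does not, since 29 new responders are needed either way. A reader might also infer a selective denominator from "Additional subjects may be enrolled and treated so as to accrue a minimum of 50 evaluable subjects with at least 2 on treatment scans". That reads as an accrual target. No analysis set in either document requires two scans, and SAP 7.5 already specifies All Treated and Response Evaluable analyses.

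**Conclusion.** The point holds in a limited form. The only ORR analysis and precision spelled out for the PD-L1-negative cohort mix the new subjects with about 18 who appear to have generated the signal. If they did, the pooled ORR is 4.0 to 5.3 points high at a true 35% to 30%, and its lower limit exceeds the truth 4.0% to 8.5% of the time instead of at most 2.5%. The bias vanishes at 50% and turns slightly negative at 56%.

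This rests on the 9/18 link, which the sponsor can confirm or deny in one sentence, and on a true rate well below 50%. ORR is secondary and nothing is formally tested, so the consequence is a possible misreading of an estimate. The documents do not support saying that the pooled analysis is invalid, that it is biased upward whatever the true rate, or that 38/68 is wrong.

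**What to change.** In Protocol 8.1.2.2 and the Synopsis:
- Commit to reporting the ORR and 95% Clopper-Pearson interval for the newly enrolled PD-L1-negative cohort on its own, in all treated subjects (the SAP 6.3 default), beside the pooled 68.
- Say that the new-cohort estimate is the one used to judge whether the earlier signal is confirmed.
- Add its precision to the planning sentence: 29/50 responders give 43.2% to 71.8%.
- State whether the 18 from Cohort 2 are the 9/18 of section 1.5.

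Carry this into the SAP when it is updated for Amendment 08.

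The cost is wording in two protocol places, one SAP paragraph and one table column, with no added subjects or visits. The separate estimate has a wider interval at the benchmark, 28.6 points for 29/50 against 24.6 for 38/68. The narrower pooled interval remains available beside it.
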